8.3.3 Clinical Safety Laboratory Assessments

Refer to Appendix 2 for the list of clinical laboratory tests to be performed and to the SoA for the timing and frequency.

- The investigator or medically qualified designee (consistent with local requirements) must review the laboratory report, document this review, and record any clinically relevant changes occurring during the study in the AE section of the CRF. The laboratory reports must be filed with the source documents. Clinically significant abnormal laboratory findings are those which are not associated with the underlying disease, unless judged by the investigator to be more severe than expected for the participant's condition.
- All protocol-required laboratory assessments, as defined in Appendix 2, must be conducted in accordance with the laboratory manual and the SoA.
- If laboratory values from nonprotocol-specified laboratory assessments performed at the institution's local laboratory require a change in study participant management or are considered clinically significant by the investigator (eg, SAE or AE), then the results must be recorded in the appropriate CRF (eg, SLAB).
- For any laboratory tests with values considered clinically significantly abnormal during participation in the study or within 14 days after the last dose of study intervention, every attempt should be made to perform repeat assessments until the values return to normal or baseline or if a new baseline is established as determined by the investigator.

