9.4.2 Safety Endpoints

A description of safety measures is contained in Section 8.3 and Section 8.4. The analysis of safety results is described in Section 9.6.2.

The safety analysis endpoints include:

- The proportion of: 1) participants with at least 1 AE; 2) participants with at least 1 drug-related AE; 3) participants with at least 1 SAE; 4) participants with at least 1 serious and drug-related AE; 5) participants who discontinued study intervention due to AE; 6) participants who discontinued study intervention due to a drug-related AE; and 7) participants with AE(s) leading to death. The AE reporting period is from the time of randomization through 14 days following cessation of treatment. Additional reporting periods will be used as appropriate (eg, throughout the study for SAE).
- Events of Clinical Interest specified in Section 8.4.7.

Predefined Limits of Change (PDLC) in Laboratory Parameters

For the summaries of laboratory tests, participants must have both a baseline and post-randomization on-treatment measurement to be included. Participants' laboratory values (based on their most abnormal laboratory test values, in the direction of interest, while on study intervention) will be classified as to whether or not they fall outside of the PDLC and are worse in grade (ie, more abnormal in the direction of interest) than at baseline. The criteria will be adapted from the DAIDS table for Grading the Severity of Adult and Pediatric Adverse Events, JUL 2017, version 2.1. A listing of the participants who meet the criteria will also be provided.

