9.5.2 Safety Analysis Populations

Safety analyses will be conducted in the APaT population, which consists of all randomized participants who received at least 1 dose of study treatment. Participants will be included in the treatment group corresponding to the study treatment they actually received for the analysis of safety data using the APaT population. This will be the treatment group to which they are randomized except for participants who take incorrect study treatment for the entire treatment period; such participants will be included in the treatment group corresponding to the study treatment actually received. Part 1 (Phase 2) and Part 2 (Phase 3) of the study will be combined for the final analysis of safety endpoints. The data presentations will focus on the selected dose group for MK-4482 and placebo.

At least 1 laboratory value or vital sign obtained subsequent to at least 1 dose of study treatment is required for inclusion in the analysis of the respective safety parameter. To assess change from baseline, a baseline measurement is also required.

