Tier 3 Events

Safety endpoints that are not Tier 1 or 2 events are considered Tier 3 events. Only point estimates by treatment group are provided for Tier 3 safety parameters.

Continuous Safety Measures

For continuous measures such as changes from baseline in laboratory and vital signs parameters, summary statistics for baseline, on-treatment, and change from baseline values will be provided by treatment group in table format. In addition, summary statistics for the difference between treatment groups will also be provided.

Table 6 Analysis Strategy for Safety Parameters

Safety Tier	Safety Endpoint ^a	p-value	95% CI for Treatment Comparison	Descriptive Statistics
Tier 1	ECIs	X	X	X
Tier 2	Any AE		X	X
	Any Serious AE		X	X
	Any Drug-Related AE		X	X
	Any Serious and Drug-Related AE		X	X
	Discontinuation due to AE		X	X
	Discontinuation due to Drug-Related AE		X	X
	Specific AEs by SOCs and PT (incidence ≥ 4 participants in at least 1 of the treatment groups)		X	X
	PDLCs ^b (incidence ≥ 4 participants in at least 1 of the treatment groups)		X	X
Tier 3	Specific AEs by SOC and PT (incidence < 4 participants in each of the treatment groups)			X
	PDLCs ^b (incidence < 4 participants in each of the treatment groups)			X
	Change from Baseline Results (Labs, Vital Signs)			X

AE=adverse event; CI=confidence interval; ECI=event of clinical interest; PT=preferred term; SOC=system organ class; PDLC=pre-defined limit of change; X=results will be provided.

^a Adverse Event references refer to both Clinical and Laboratory AEs.

^b Includes only those endpoints not pre-specified as Tier 1 or not already pre-specified as Tier-2 endpoints.

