10.3.4 Recording AE and SAE

AE and SAE recording

- When an AE/SAE occurs, it is the responsibility of the investigator to review all documentation (eg, hospital progress notes, laboratory, and diagnostics reports) related to the event.
- The investigator will record all relevant AE/SAE information on the AE CRFs/worksheets at each examination.
- It is not acceptable for the investigator to send photocopies of the participant's medical records to the Sponsor in lieu of completion of the AE CRF page.

- There may be instances when copies of medical records for certain cases are requested by the Sponsor. In this case, all participant identifiers, with the exception of the participant number, will be blinded on the copies of the medical records before submission to the Sponsor.
- The investigator will attempt to establish a diagnosis of the event based on signs, symptoms, and/or other clinical information. In such cases, the diagnosis (not the individual signs/symptoms) will be documented as the AE/SAE.

Assessment of intensity/toxicity

- An event is defined as “serious” when it meets at least 1 of the predefined outcomes as described in the definition of an SAE, not when it is rated as severe.
- The investigator will make an assessment of intensity for each AE and SAE (and other reportable safety event) by recording the grade according to the NIH DAIDS Table for Grading the Severity of Adult and Pediatric Adverse Events, version 2.1. Any AE which changes DAIDS grade over the course of a given episode will have each change of grade recorded on the AE CRFs/worksheets.

Grade 1 Mild event: Mild symptoms causing no or minimal interference with usual social and functional activities with intervention not indicated.

Grade 2 Moderate event: Moderate symptoms causing greater than minimal interference with usual social and functional activities with intervention indicated.

Grade 3 Severe event: Severe symptoms causing inability to perform usual social and functional activities with intervention or hospitalization indicated.

Grade 4 Potentially life-threatening event: Potentially life-threatening symptoms causing inability to perform basic self-care functions with intervention indicated to prevent permanent impairment, persistent disability, or death.

Grade 5 Death: Deaths related to an AE.

Assessment of causality

- Did the Sponsor’s product cause the AE?

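### The PDLC laboratory tables in Section 9.4.2 grade on-treatment values only, so the Day 10 and Day 15 draws stay out of the graded comparison although they fall inside the 14-day AE period

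*Combined protocol and SAP*

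**What the plan says.** Section 9.4.2 sets two conditions for the PDLC summaries. On inclusion, "participants must have both a baseline and post-randomization on-treatment measurement to be included". On grading, each participant is classified on the "most abnormal laboratory test values, in the direction of interest, while on study intervention", against criteria adapted from the DAIDS table and only if the grade is worse than at baseline. A listing of those who meet the criteria is also planned.

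The same section sets a longer period for adverse events: "The AE reporting period is from the time of randomization through 14 days following cessation of treatment".

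Three other places bear on the point:

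- Section 9.5.2, on who may enter a laboratory analysis: "At least 1 laboratory value or vital sign obtained subsequent to at least 1 dose of study treatment is required for inclusion".
- Section 9.6.2, on continuous measures: "summary statistics for baseline, on-treatment, and change from baseline values will be provided by treatment group in table format". The same section and Table 6 give PDLCs a between-arm 95% CI when at least 4 participants in a group are affected, and descriptive statistics otherwise.
- Section 1.3 defines EOT as the day of the last dose and schedules central hematology and chemistry on Day 1, Day 3, EOT, Day 10, Day 15 and Day 29.

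Neither the protocol nor the SAP defines on-treatment in days or extends it past the last dose.

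**The concern.** Treatment lasts five days, but the laboratory schedule runs to Day 29. A rule limited to on-treatment values therefore leaves most of the post-baseline draws ungraded. Two of the omitted draws, Day 10 and Day 15, fall where the plan is still collecting adverse events.

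The PDLC table compares arms on grades taken from the laboratory values themselves, without an investigator's judgement in between. If a graded shift first appears after the last dose and no investigator reports it, this table is the natural place to see it, and as written it will not. At stake is the completeness of a descriptive safety display. The primary efficacy conclusion is not touched.

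**Working it through.** The plan prints no count of draws entering the PDLC tables, so there is no such figure to reproduce. The printed figure that depends on the draw schedule is the blood volume in Appendix 2, Table 12, and it serves to confirm the draws.

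**1. Number of draws.** Table 12 gives visit totals of 23 (Day 1), 4.5 (Day 3), 29 (EOT), 23 (Day 10), 4.5 (Day 15) and 24 mL (Day 29).

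23 + 4.5 + 29 + 23 + 4.5 + 24 = 108 mL, as printed. Adding 32 mL for the PBMC cohort gives 140 mL, also as printed. Hematology and chemistry volumes appear at all six visits, so there is 1 baseline draw and there are 5 post-baseline draws.

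**2. Day of last dose.** Section 8.1.8.1 gives the day of the tenth dose by start time. The visit windows in Section 1.3 are Day 3 ± 24 h (Days 2–4), Day 10 ± 1 (Days 9–11), Day 15 + 3 (Days 15–18) and Day 29 + 3 (Days 29–32).

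| First dose | Last dose (EOT) | Last dose + 14 | Day 10 draw, days after last dose | Day 15 draw | Day 29 draw |
|---|---|---|---|---|---|
| Day 1 morning | Day 5 | Day 19 | 4–6 | 10–13 | 24–27 |
| Day 1 evening or Day 2 morning | Day 6 | Day 20 | 3–5 | 9–12 | 23–26 |
| Day 2 evening | Day 7 | Day 21 | 2–4 | 8–11 | 22–25 |

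**3. Draws graded, full course.**

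- On treatment, as written: Day 3 and EOT, 2/5 = 40%.
- Through 14 days after the last dose: Day 3, EOT, Day 10 and Day 15, 4/5 = 80%. This holds for every start time, because the latest Day 15 visit (Day 18) precedes the earliest window end (Day 19).
- Through Day 29: 5/5.

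**4. Early stops.** With the last dose on Day 1, the Day 3, 10, 15 and 29 draws are all off treatment, since the earliest Day 3 draw is on Day 2. Only the EOT draw that Section 8.11.3 asks for at discontinuation can enter. If it is taken on the day of the last dose, the Section 1.3 definition makes it on-treatment; if it is taken later, the plan gives no rule. With the last dose on Day 2 or 3, the Day 3 draw counts only if taken by that day. Under a 14-day window, last doses on Days 1, 2 and 3 give ends on Days 15, 16 and 17, so the Day 15 draw enters if taken by then. From a last dose on Day 4 (4 + 14 = 18) it always enters.

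**5. What else would show a Day 10 or Day 15 abnormality.**

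- Events of clinical interest (Section 8.4.7): the combined liver pattern, and any post-baseline platelet value below 50,000/µL.
- Laboratory adverse events: under Section 8.3.3 the investigator must "record any clinically relevant changes occurring during the study in the AE section of the CRF", and Section 10.3.4 requires "recording the grade according to the NIH DAIDS Table for Grading the Severity of Adult and Pediatric Adverse Events, version 2.1". Table 6 counts laboratory adverse events among AEs, with between-arm 95% CIs when at least 4 participants in a group are affected.

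What remains uncovered in graded form is a later shift that meets neither event-of-clinical-interest criterion and is not judged clinically relevant. The documents give neither the number of early stops nor the share of shifts first seen on Day 10 or 15, so no count of missed events can be derived.

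**The case against.** The strongest reply is that an on-treatment window may be deliberate. Section 9.4.2 states the adverse event period and the PDLC window separately, and different windows for the two are not in themselves an error. Values taken on treatment are also less exposed to disease course and to later therapies. The table is descriptive, and important late abnormalities have the other routes listed above. All of this stands, and it makes the point an improvement rather than a correction.

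A reader might also draw four stronger conclusions that the documents do not support:

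- *Sections 9.4.2 and 9.5.2 contradict each other.* Section 9.5.2 sets a minimum for entry and Section 9.4.2 adds a stricter condition for laboratory summaries. Both can be followed, and a cross-reference is enough.
- *Section 8.3.3 sets a 14-day laboratory analysis window.* It does not. It asks for repeat testing of values found "clinically significantly abnormal during participation in the study or within 14 days after the last dose of study intervention". The support for 14 days comes from the adverse event period in Section 9.4.2.
- *Continuous laboratory summaries also stop at the last dose.* Section 9.6.2 names on-treatment values and change from baseline as separate items, and Table 6 lists change from baseline with no window. Later changes may still be summarised.
- *A delayed toxicity is being missed.* The marrow changes in Section 4.3.1 arose under continuous dosing in a 28-day dog study. The post-dose lipase elevations in Section 4.2.1.2 were as frequent on placebo. Section 4.3.3 reports no clinically meaningful hematological, pancreatic or hepatic abnormality by dose or treatment in Part 1.

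**Conclusion.** The point holds in a limited form. As written, 2 of 5 scheduled post-baseline draws are graded for a full-course participant, against 4 of 5 under the 14-day period that the same section uses for adverse events. The loss is confined to later graded shifts that neither the events of clinical interest nor investigator-reported laboratory adverse events would pick up. Separately, the status of a discontinuation-visit draw taken after the last-dose day is undefined.

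This rests on the plain meaning of the on-treatment wording. The sSAP, which is not among the documents reviewed, may define the term differently. No number of missed events is claimed. It is a cheap improvement worth making, because the samples are already scheduled for central analysis in both arms.

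**What to change.** Through the sSAP, before Part 2 is unblinded:

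1. Add a PDLC table graded on the most abnormal post-baseline value through 14 days after the last dose, requiring a baseline and at least one post-baseline value in that window.
2. Keep the on-treatment PDLC table beside it.
3. Define on-treatment once, and state how a discontinuation-visit draw taken after the last-dose day is classified.
4. Cross-reference Sections 9.4.2, 9.5.2 and 9.6.2, and state the window for change-from-baseline summaries.

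Section 9 allows changes to non-confirmatory analyses by this route, and no extra samples are needed. The cost is one table and some wording.

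The drawback is confounding of the later values. Section 9.9.1 assumes 12% versus 6% hospitalized or dying, which at 775 per arm is 0.12 × 775 = 93 on placebo against 0.06 × 775 = 46.5 on MK-4482. Section 6.5 (Table 2) permits other COVID-19 therapies once a participant is hospitalized. Disease course and co-treatment could thus differ between arms and mask or mimic a drug effect, which is why neither table should be read alone.

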9.5 Analysis Populations

9.5.1 Efficacy Analysis Populations

The MITT population will serve as the primary population for the analysis of efficacy data for both parts of this study. The MITT population consists of all randomized participants who received at least 1 dose of study intervention. Part 1 (Phase 2) and Part 2 (Phase 3) of the study will be analyzed separately for efficacy endpoints. Therefore, the MITT population for Part 2 will not include Part 1 participants, and vice versa.

A supportive analysis using the Per-Protocol population will be performed for the primary efficacy endpoint(s) for Part 2. The Per-Protocol population excludes participants due to deviations from the protocol that may substantially affect the results of the primary efficacy endpoint.

The final determination on protocol deviations, and thereby the composition of the Per-Protocol population, will be made prior to the final unblinding of the database and will be documented in a separate memo.

Participants will be included in the treatment group to which they are randomized for the analysis of efficacy data using both the MITT and Per-Protocol populations.

9.5.2 Safety Analysis Populations

Safety analyses will be conducted in the APaT population, which consists of all randomized participants who received at least 1 dose of study treatment. Participants will be included in the treatment group corresponding to the study treatment they actually received for the analysis of safety data using the APaT population. This will be the treatment group to which they are randomized except for participants who take incorrect study treatment for the entire treatment period; such participants will be included in the treatment group corresponding to the study treatment actually received. Part 1 (Phase 2) and Part 2 (Phase 3) of the study will be combined for the final analysis of safety endpoints. The data presentations will focus on the selected dose group for MK-4482 and placebo.

At least 1 laboratory value or vital sign obtained subsequent to at least 1 dose of study treatment is required for inclusion in the analysis of the respective safety parameter. To assess change from baseline, a baseline measurement is also required.

9.6 Statistical Methods

This section describes the statistical methods that address the primary and secondary objectives as well as a key exploratory objective for viral RNA endpoints. Methods related to other exploratory objectives will be described in the sSAP. Methods related to PK analysis and PK/PD modeling will be described in a separate modeling and simulation plan authored by QP2. Methods related to dose-response analysis using MCP-MOD will be described in a separate dose-response analyses plan. Methods related to analyses of biomarkers and other exploratory samples will be described separately.

Efficacy results that will be deemed to be statistically significant after consideration of the type I error control for interim analyses are discussed in Section 9.7. There are no adjustments for multiplicity. Statistical testing and inference for safety analyses are described in Section 9.6.2.

9.6.1 Statistical Methods for Efficacy Analyses

For the evaluation of the primary hypothesis, superiority of MK-4482 compared to placebo with respect to the percentage of participants with either hospitalization or death by Day 29 will be assessed using the stratified Miettinen and Nurminen method [Miettinen, O. 1985]. Superiority will be concluded based on p-value boundaries as described in Section 9.7. Stratification factors include the stratification factors specified in Section 6.3.2. Geographic region will not be used as a stratification factor in the primary analyses, but it may be considered as an additional stratification factor of the stratified Miettinen and Nurminen method for sensitivity analysis if it does not cause sparse data issues. The number of regions along with the specific countries contained within each region will be described in the sSAP. Every effort will be made to ascertain hospitalization and survival status for all participants. For the primary analysis of this endpoint in the MITT population, unknown Day 29 survival status will be treated as failure, and early withdrawal from the study with known Day 29 survival status as alive but unknown Day 29 hospitalization status will not be treated as failure. A sensitivity analysis treating both unknown Day 29 survival status and early withdrawal from the study with known Day 29 survival status as alive but unknown Day 29 hospitalization status as failure will also be provided.

A sensitivity analysis for the primary endpoint will be conducted that includes only COVID-19 related hospitalizations or death by Day 29 in the MITT population. This treatment comparison will be assessed using the stratified Miettinen and Nurminen method as described above. An additional sensitivity analysis excluding hospitalizations that occur early in the course of the study (ie, within a certain time from randomization) will also be performed. Details will be specified in the sSAP.

Two additional sensitivity analyses will be performed using the endpoints of time to hospitalization/death and time to COVID-related hospitalization/death. These analyses will be performed in the MITT population. The stratified log-rank test will be used for the comparison of MK-4482 with placebo for these 2 endpoints. Stratification factors will be the same as those used for the primary endpoint. Hazard ratios will be based on the stratified Cox Proportional Hazards regression model. The Efron approximation will be used for handling ties. Hazard ratios less than 1 indicate a benefit for MK-4482. Censoring rules for these analyses will be specified in the sSAP.

Time to sustained resolution or improvement and time to progression of each targeted self-reported sign/symptom of COVID-19 will be summarized using data collected from a 15-item daily paper symptom diary completed by participants (Section 8.2.5). The distribution of time to sustained resolution or improvement and time to progression of each sign/symptom will be analyzed using the same method for the time to hospitalization or death endpoint, ie, the stratified log-rank test will be used for the comparison of MK-4482 with

placebo and the Cox proportional hazard model will be used to estimate the hazard ratio. Descriptive statistics and Kaplan-Meier plots will also be provided.

The proportion of participants with each sign/symptom will be summarized by severity (or presence/absence for loss of taste and loss of smell) for each treatment group at Day 1, Day 3, EOT, Day 10, Day 15, and Day 29.

These summaries above will include comparison of each individual sign/symptom. Missing symptom diary data will be imputed using LOCF method. Additional details will be specified in the sSAP.

The viral RNA endpoints at earlier time points (Day 3 and EOT) will be important for the dose selection decision from Part 1 of the study. Change from baseline in SARS-CoV-2 RNA titer, calculated as \log_{10} (post) minus \log_{10} (baseline), as measured by quantitative RT-PCR of samples from NP (Parts 1 and 2) and OP (Part 1 only) swabs will be summarized separately by treatment group and time point. The DAO approach will be used to handle missing data for these summary statistics. In addition to summary statistics, treatment differences in change in SARS-CoV-2 RNA titer from baseline over time will be estimated using longitudinal models. Graphical presentations of the change from baseline will be presented and the impact of baseline viral RNA level will be explored using subgroup analyses (defined by level of baseline viral RNA) and analyses/summaries that exclude participants with low baseline levels (eg, viral RNA $<10^6$ copies/mL).

Percentage of participants with undetectable viral RNA (below limit of detection) as measured by qualitative RT-PCR of samples from NP (Parts 1 and 2) and OP (Part 1 only) swabs will be summarized separately by treatment group and time point. Between-treatment differences and 95% CIs will be estimated using the stratified Miettinen and Nurminen method [Miettinen, O. 1985].

WHO 11-point ordinal scale score will be analyzed using the cumulative logits function and the proportional odds model as described by McCullagh [McCullagh, P. 1980]. This methodology provides an estimate of the common odds ratio for assessing differences between treatment groups. In addition to a term for treatment group, the model will include terms for the stratification factors specified Section 6.3.2. The WHO 11-point ordinal scale will be determined based on relevant data collected in eCRFs.

A detailed analysis strategy for key efficacy endpoints is listed in [Table 5](#).

Table 5 Analysis Strategy for Key Efficacy Endpoints

Endpoint/Variable (Description, Time point)	Primary vs. Supportive Approach ^a	Statistical Method ^b	Analysis Population	Missing Data Approach
Primary				
Proportion of participants with either hospitalization or death by Day 29	P	Stratified Miettinen and Nurminen ^c	MITT	As described in 9.6.1
Proportion of participants with either hospitalization or death by Day 29	S	Stratified Miettinen and Nurminen ^c	PP	Observed data only
Proportion of participants with either COVID-related hospitalization or death by Day 29	S	Stratified Miettinen and Nurminen ^c	MITT	M=F ^d
Proportion of participants with either COVID-related hospitalization or death by Day 29	S	Stratified Miettinen and Nurminen ^c	PP	Observed data only
Time to hospitalization or death by Day 29	S	Stratified log-rank test ^e ; Stratified Cox proportional hazard regression ^f	MITT, PP	Model-based with censoring
Time to COVID- related hospitalization or death by Day 29	S	Stratified log-rank test ^e ; Stratified Cox proportional hazard regression ^f	MITT, PP	Model-based with censoring
Secondary				
Time to sustained resolution or improvement of each targeted self-reported sign/symptoms of COVID-19	P (MITT) S (PP)	Stratified log-rank test ^e ; Stratified Cox proportional hazard regression ^f	MITT PP	Model-based with censoring
Time to progression of each targeted self-reported sign/symptom of COVID-19	P (MITT) S (PP)	Stratified log-rank test ^e ; Stratified Cox proportional hazard regression ^f	MITT PP	Model-based with censoring
Odds of a more favorable response on the WHO 11-point ordinal scale on Day 3, EOT, Day 10, Day 15, and Day 29	P (MITT) S (PP)	Proportional odds model ^g	MITT PP	Model-based
EOT= end of treatment; F= failure; M= missing; MITT= modified intent-to-treat; PP= per-protocol; WHO= World Health Organization.				
^a P=Primary approach; S=Supportive approach.				
^b Statistical models are described in further detail below:				
^c Miettinen and Nurminen method stratified by the factors specified in Section 6.3.2.				
^d M=F is Missing equals to Failure				
^e The stratified log-rank test includes stratification factors specified in Section 6.3.2				
^f Stratified Cox Proportional Hazards regression includes terms for treatment, stratification factors specified in Section 6.3.2				
^g Proportional odds model includes terms for treatment and stratification factors specified in Section 6.3.2.				

